4.3.1 Measures of Primary Outcome

The Core Laboratory will perform measurements and calculations on the echo images based on recent guidelines by the American Society of Echocardiography Pediatric and CHD Council (1). The measurements and calculations will be adjusted for the effects of BSA, age, gender, and race. The following two-dimensional measurements will be performed for each submitted study:

- Mitral valve annular anteroposterior diameter
- Mitral valve annular lateral diameter
- Tricuspid valve annular anteroposterior diameter
- Tricuspid valve annular lateral diameter
- Aortic valve annular diameter
- Aortic root diameter
- Aortic sinotubular junction diameter
- Ascending aortic diameter
- Proximal transverse arch diameter
- Distal transverse arch diameter
- Aortic isthmus diameter
- Left main coronary arterial diameter
- Proximal left anterior descending coronary arterial diameter
- Proximal right coronary arterial diameter
- Pulmonary valve annular diameter
- Main pulmonary arterial diameter
- Right pulmonary arterial diameter
- Left pulmonary arterial diameter
- Left ventricular short-axis end-diastolic diameter (LVEDD)
- Left ventricular short-axis end-diastolic posterior wall thickness
- Left ventricular short-axis end-diastolic septal wall thickness
- Left ventricular short-axis end-systolic diameter (LVESD)
- Left ventricular long-axis end-diastolic length (LVEDL)
- Left ventricular long-axis end-diastolic epicardial length (LVEDL_{epi})
- Left ventricular long-axis end-systolic length (LVESL)
- Left ventricular short-axis end-diastolic area (LVEDA)
- Left ventricular short-axis end-diastolic epicardial area (LVEDA_{epi})
- Left ventricular short-axis end-systolic area (LVESA)

The following calculations will also be performed on the same set of measurements when available for each submitted study:

- Left ventricular shortening fraction = $(LVEDD - LVESD)/LVEDD$
- Left ventricular end-diastolic volume (LVEDV) = $(5/6)(LVEDA)(LVEDL)$
- Left ventricular end-diastolic epicardial volume (LVEDV_{epi}) = $(5/6)(LVEDA_{epi})(LVEDL_{epi})$
- Left ventricular end-systolic volume (LVESV) = $(5/6)(LVESA)(LVESL)$
- Left ventricular ejection fraction = $(LVEDV - LVESV)/LVEDV$
- Left ventricular mass = $(1.05)(LVEDV_{epi} - LVEDV)$

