5.4 Subject Availability

Several centers were polled to determine the number of eligible patients that would have been available from the 2011 hospital and/or echo database:

Site	Eligible Patients in 2011
Wisconsin	650
Montefiore	550
Boston	>300
CHOP	300
Columbia	300
Utah	250
Total	>2350

Therefore, the total sample size (as discussed in Section 6.2) can be fulfilled by having a minimum of 15 participating centers review their database since the availability of the DICOM format and submit data and echo images on 250 eligible patients. In order to optimize

geographic, racial, and ethnic diversity, it may be desirable to increase the number of sites beyond this minimum number to as many as 25.

The US Census Bureau published the following statistics regarding the racial distribution in the United States for the year 2010: 72% Whites, 13% African-Americans, and 15% in the Other category. Because of the potential problem of recruiting non-White patients for the project, several centers were polled to assess the racial distribution in their eligible patients from 2011, and the data are listed in the table below:

Site	Whites	African-Americans	Other
US Census	72%	13%	15%
Montefiore	24%	38%	39%
CHOP	50%	50%	

Based on these numbers, the target sample size and appropriate racial diversity needed for the study are both feasible as long as the racial distributions at the participating centers are determined at the outset of the project.

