6. STATISTICS

6.1 Statistical Analysis Plan

BSA for each subject will be calculated using the Haycock formula (27). The distribution of BSA and each echo measurement will be assessed and tested for normality. Any variable found to be skewed or otherwise non-normal will be transformed appropriately in order to obtain a normal (or close to normal) distribution. The analysis will require classification of each subject within one of 36 study groups based on:

- 6 age categories
 - <1 month old
 - 1 month old – <3 years old
 - 3 – <6 years old
 - 6 – <12 years old
 - 12 – <16 years old
 - 16 – 18 years old

- 2 gender categories
 - Male
 - Female
- 3 race categories
 - White
 - African-American
 - Other

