Once the best available method for obtaining BSA has been determined and the simplest, best-fit model has been identified for each of the variables, the next step will involve examination for non-constant variance (heteroscedasticity) for each regression. In general, all of these relationships are anticipated to manifest heteroscedasticity characterized by a progressively but not necessarily linearly increasing variance with increasing BSA. Under these circumstances, the method described by Altman (33) provides a simple and adequate approach to generate a constant variance relationship. Although more complex methods (log or other transforms of one or both variables) have been described, they lack a physiologic basis and do not generally outperform the Altman technique. If there are individual variables for which the Altman methodology fails to adequately eliminate heteroscedasticity, the Lambda-Mu-Sigma method described by Cole and colleagues (34) will be adopted for those specific variables.

The Z-scores for each of the 36 study groups (based on age, gender, and race) will be compared using a t-test and adjusted for multiple comparisons. Groups which are not statistically different may be combined. For example, if the Z-scores for a particular measurement are not statistically different between males and females, the two groups may be combined and a new estimate of the mean and SD for the combined group will be determined.

The potential relationship of each set of Z-scores to height, weight, and BMI will also be examined using linear regression, and the potential for differences related to ethnicity will be examined using analysis of variance.

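### Race and ethnicity are compared without centre, although race mix and the way normal children are found differ between centres, so centre differences can appear as, or mask, race differences

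*Protocol*

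**What the plan says.** Only the protocol is at hand. Its Section 6.1 is headed as the statistical analysis plan and names the tests.

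- **Classification (6.1).** "The analysis will require classification of each subject within one of 36 study groups based on" six age bands, two genders and three race categories. Centre is not a factor.
- **Adjustment (4.3.1).** "The measurements and calculations will be adjusted for the effects of BSA, age, gender, and race". Centre is not listed.
- **Comparison (6.1.2).** Z-scores of the 36 groups "will be compared using a t-test and adjusted for multiple comparisons", and "the potential for differences related to ethnicity will be examined using analysis of variance".
- **Use of the result (6.1.2).** "Groups which are not statistically different may be combined", with a new mean and SD for the combined group.
- **Centres (5.4).** The plan needs "a minimum of 15 participating centers" and may use as many as 25. The Census split is "72% Whites, 13% African-Americans, and 15% in the Other category". One polled centre reports 24% White, 38% African-American and 39% Other; a second reports 50% White. The race targets are called "feasible as long as the racial distributions at the participating centers are determined at the outset of the project".
- **Finding the children (5.5, 4.3).** Some centres search the echo database and others the hospital database. Where race is not routinely recorded, it is obtained by letter to the family.

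In Section 6, site appears only for data queries, monitoring and image quality (6.4). The limitations in Section 10 do not mention centre.

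**The concern.** The design fixes equal numbers per race category: 12 age-gender groups of 100, or 1200 children each. A centre with a high share of non-White patients will tend to supply more of two categories and less of the third. Race is then associated with centre.

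Centres can also differ in ways that shift a measurement: who is referred, how normal children are identified, which equipment and views are used. Reading by a Core Laboratory removes reader differences, but not differences in referral or acquisition, because the images were acquired locally in past care. Section 3.2 itself puts reliance on single sites first among the causes of disagreement between published Z-scores.

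An unadjusted test attributes any such centre difference to race. Because the result decides which groups may be merged, it shapes the published reference values. A spurious difference keeps race-specific references that are not needed; a masked one merges groups that do differ. Section 10 claims enough power for the White versus African-American comparison, but power does not remove this bias.

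**Working it through.** **The plan's own figures (6.2) reproduce.** With n = 80, the width of the 95% interval for the SD is √79 × (1/√χ²(0.025; 79) − 1/√χ²(0.975; 79)) = 0.319 of the SD (stated 32%). The margin for the mean is 1.96/√80 = 0.219 SD (stated 22%). N = 36 × 100 = 3600. Measurable children per race: 12 × 80 = 960.

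**How much of a centre difference passes into a race contrast.** Assume two centre types contributing equal numbers.

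- *The two polled centres, White versus non-White.* Share from the first centre: Whites 24/(24 + 50) = 32.4%; non-Whites 76/(76 + 50) = 60.3%. Transfer: 0.603 − 0.324 = 0.28 of any offset between the centres.
- *First polled centre against a Census-like centre, African-American versus White.* The first centre's row sums to 101%, so divide by 101. Whites: 0.238/(0.238 + 0.72) = 24.8%. African-Americans: 0.376/(0.376 + 0.13) = 74.3%. Transfer: 0.743 − 0.248 = 0.50.

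**False-positive rate with 15 centres and no true race effect.** Assumptions: centre effects have SD τ in Z units (range shown) and the within-centre SD is 1. The stepped mix has 3 centres at White:African-American 24:38, 2 at 50:50 and 10 at 72:13. Each race is spread over centres in proportion to these figures.

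- Whites sum to 3×24 + 2×50 + 10×72 = 892; African-Americans to 3×38 + 2×50 + 10×13 = 344.
- Shares per centre: Whites 0.0269, 0.0561, 0.0807; African-Americans 0.1105, 0.1453, 0.0378.
- S = Σ(difference in shares)² = 3(0.0836)² + 2(0.0893)² + 10(0.0429)² = 0.0553.
- The spurious race difference has SD τ√S = 0.235τ, that is 0.024 to 0.071 Z for τ = 0.10 to 0.30.
- The test statistic is inflated by R = √(1 + τ²S/(2/n)), and the rejection rate is 2 × [1 − Φ(z/R)], with z = 1.96, or 2.394 for Bonferroni over three race contrasts (nominal 1.7%).

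| τ | R, n = 960 | 5% test, 960 v 960 | Bonferroni over 3, 960 v 960 | 5% test, 80 v 80 |
|---|---|---|---|---|
| 0.10 | 1.125 | 8.1% | 3.3% | 5.3% |
| 0.15 | 1.264 | 12.1% | 5.8% | 5.6% |
| 0.20 | 1.436 | 17.2% | 9.6% | 6.0% |
| 0.30 | 1.841 | 28.7% | 19.4% | 7.4% |

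Simulations of the same set-up gave 7–9%, 11–13%, 17–20% and 27–30% at 960 per race, and 5.4%, 5.3%, 5.9% and 8.0% at 80. With centre in the model the rate was 4–6%.

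**Sensitivity to the mix.** If the 15 centres are graded evenly from the first polled centre's mix to the Census mix, simulation at 960 per race gives 6.0%, 11.2% and 16.1% for τ = 0.1, 0.2 and 0.3, against 4.5%, 5.4% and 4.9% with centre in the model. If the second polled centre's non-White half is split equally between the two other categories (50:25), the rates for the four values of τ are about 8%, 11%, 15% and 25%.

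**Cost in precision.** In the stepped mix, within-centre information on race relative to the unadjusted contrast is Σ[pA·pW/(pA + pW)]/0.5 = (3×0.0216 + 2×0.0405 + 10×0.0257)/0.5, about 0.80. The standard error grows by 1/√0.80 = 1.12.

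**The case against.** The strongest reply is that the large rates belong to a comparison the protocol does not clearly specify. Section 6.1.2 compares 36 groups of about 80 measurable children and adjusts for multiplicity. For such a cell pair the rate is 5 to 8% before adjustment, and at most 0.5% after Bonferroni over 36 comparisons (nominal 0.05/36 = 0.14%). This stands for single cells. It does not settle the matter, because the section's own example of merging males with females points to comparisons over wider groups. The adjustment lowers how often a false difference is declared but does not remove the bias.

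Other replies also carry weight:

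- The spurious difference, about 0.02 to 0.07 Z, is small beside the 0.22 SD margin accepted for each group mean.
- Separate race groups are the default, so a false positive only leaves that default in place. The masking direction does not have this protection.
- The centre mixes and the centre SD are assumed. The Census row is not a centre, and the second polled centre does not split its non-White children.
- A centre term may be given in a separate analysis plan. However, Section 6.1 already fixes the tests.

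A reader might infer that the race targets have to be met by a few centres. The documents do not support that. 1200/15 = 80 children per race per centre; at the smallest polled yield (250 in 2011) and the Census 13%, a centre would see about 32 eligible African-American children a year, or about 130 over 2008–2011 if 2011 is typical. Equal supply looks possible; the protocol simply does not require it. A reader might also infer that centre differences are certain to be reported as race effects. No centre difference is documented, so they can be, and no more.

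**Conclusion.** The point holds as a plausible bias that is avoidable at low cost, not as a demonstrated error in the results. The text establishes the missing centre term, the differing race mix and the differing identification routes. The size rests on assumptions: centre SD 0.10 to 0.30 Z, a 15-centre mix built from two polled centres and the Census row, and no true race effect. On these, the false-positive rate is about 6 to 30% for a race contrast pooled over age and gender and about 5 to 8% for single cells, against about 5% once centre is modelled. With Bonferroni over three race contrasts, the pooled rate in the stepped mix is about 3 to 19% against a nominal 1.7%.

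It would go too far to apply the pooled figures to the cell-by-cell tests, or to claim the same confounding for ethnicity. No ethnicity mix by centre is given, and Section 10 already expects low power there. The ethnicity part rests only on the absence of a centre term.

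**What to change.** For the race comparison that decides whether groups are merged:

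1. Replace the simple t-test by a regression of Z-scores, pooled over the age and gender groups, on race with a centre intercept (fixed or random). Take these Z-scores from a reference not split by race, since scores standardised within each race group average zero by construction.
2. Keep the planned multiplicity adjustment.
3. For each measurement, report race-by-centre counts and the between-centre SD.
4. Use the same centre term for ethnicity.

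The plan has no pooled model at present, so this is a short new model specification rather than one added covariate. Section 6.5 already provides for documenting such a change. The group means and SDs for the reference values are still derived as in 6.1.1; a within-centre contrast does not itself supply them, and they continue to reflect the mix of contributing centres.

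Cost: a standard error for the race contrast about 12% larger under the stepped mix. The contributing site is known for each submission, so no new data are needed, and N stays 3600.

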6.2 Number of Subjects to be Enrolled

Sample size calculations were performed to determine the number of patients needed for each of the 36 study groups that will provide reasonable estimates of the population mean and SD for each measurement (35). There are several assumptions associated with these calculations:

- All variables should be normally distributed. Any variable that does not meet the normality assumption will need to undergo a mathematical transformation.
- At least 80% of the submitted echo studies will contain all the necessary images to perform each of the study measurements. In other words, for every group of 100 study patients, one would expect at least 80 studies in which each particular measurement can be made.

Assuming a normal distribution, a confidence interval for the SD is given by the following equation:

$$\sqrt{\frac{(n-1)s^2}{\chi_{n-1}^{2(1-\frac{\alpha}{2})}}} \leq \sigma \leq \sqrt{\frac{(n-1)s^2}{\chi_{n-1}^{2(\frac{\alpha}{2})}}}$$

We can minimize the width and solve for n such that

$$\sqrt{n-1} \left(\frac{1}{\sqrt{\chi_{n-1}^{2(\frac{\alpha}{2})}}} - \frac{1}{\sqrt{\chi_{n-1}^{2(1-\frac{\alpha}{2})}}} \right) < r$$

where r is some proportion of the observed point estimate of the SD. For $n = 80$ and $\alpha = 0.05$, the width of a 95% confidence interval would be 32% ($r = 0.32$) of the observed SD. In addition, the margin of error is calculated as

$$\frac{z_{\frac{\alpha}{2}} \sigma}{\sqrt{n}}$$

For $n = 80$, the margin of error for the mean would be 22% of the observed SD. Given the 80% echo quality assumption discussed above, each of the 36 study groups should have 100 patients in order to satisfy the requirements for the 95% confidence interval and margin of error for the mean. Thus the total sample size for the study is 3600 patients.

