6.3 Level of Significance

The primary aim of this study will be the estimation of the mean and SD of the normal population for the measurements listed in Section 4.3.1. When hypothesis testing is conducted for some secondary aims, the type I error probability will be 0.05. No adjustment will be made to account for comparing the groups with respect to more than one outcome variable. However, multiple comparison adjustments will be made to control the type I error when comparing study groups for the purpose of collapsing group categories.

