10. STUDY LIMITATIONS

- There are inherent limitations associated with self-reported race and ethnicity within a retrospective study. Most centers collect these data when patients are evaluated and undergo testing, and the accuracy of the data is determined purely by patient response on standard hospital intake forms.
- The Other race category encompasses Asians, Pacific Islanders, Native Americans, and those from multiracial origins. The study will have enough power to determine

differences in normal echo reference values between Whites and African-Americans. There are limitations associated with combining all the other races in the third category, but creating study groups with each of the other racial categories is not feasible within the context of cost, time, and racial distribution at the participating centers.

- Although there are no reports of differences in normal echo reference values between Hispanics and non-Hispanics, a secondary analysis to see if there are differences between the two populations in the study will be performed. Although it is not likely that the study will have enough power to fully determine these differences, the project will establish the framework for future studies to evaluate this and other similar questions.
- Among the exclusion criteria are documented family history of cardiomyopathy and documented first degree relative with congenital left-sided heart disease. There will likely be patients for whom this documentation is not available, and some patients might be erroneously included in the study population. Given that most of the echocardiograms for the study will be normal, the effect of including some of these patients into the analysis will hopefully be negligible.

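### Groups may be merged on a non-significant, multiplicity-adjusted t-test alone: merging groups that truly differ is not controlled, and group SDs are not compared

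*Protocol*

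**What the plan says.** Protocol Section 6.1.2 takes the Z-scores of the 36 groups, which "will be compared using a t-test and adjusted for multiple comparisons", and continues: "Groups which are not statistically different may be combined". Its example is a measurement on which males and females do not differ statistically. The two may then be pooled and given one new mean and one new SD.

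Section 6.3 sets the level for secondary hypothesis tests ("the type I error probability will be 0.05") and adds that "multiple comparison adjustments will be made to control the type I error when comparing study groups for the purpose of collapsing group categories". The adjustment method and the number of comparisons are not stated.

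Section 6.2 sizes the groups for the precision of each group's mean and SD. It says that "each of the 36 study groups should have 100 patients", and that of every 100 "one would expect at least 80 studies in which each particular measurement can be made". No difference of interest, equivalence margin or power for the merging step appears anywhere in the protocol.

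**The concern.** In most testing the error to guard against is declaring a difference that is not there. Here the decision runs the other way: the action, merging, follows from not finding a difference. The error that harms the reference values is missing a real difference (type II). Section 6.3 controls the opposite error, and every added comparison raises the bar for keeping groups apart.

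The test also covers only half of the product. The primary aim is a mean and an SD, yet a t-test compares means only. The variance check in Section 6.1.2 concerns spread against BSA within each regression, not spread between groups. No stated step compares group SDs before one common SD replaces them.

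At stake is the Z-score itself. If groups that differ are merged, the higher group is flagged as abnormal too often at the upper end and the lower group too rarely. Section 3.2 lists failure to adjust for gender and race among the defects of earlier databases, and this rule can bring that defect back.

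**Working it through.** **1. The plan's own figures (Section 6.2), n = 80.**
- Width of the 95% CI for the SD: √79 × (1/√56.31 − 1/√105.47) = 0.319, stated as 0.32.
- Margin of error for the mean: 1.96/√80 = 0.219 SD, stated as 22%.
- 80/0.8 = 100 per group; 36 × 100 = 3600.

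All reproduce. They are precision figures for single groups, not power for comparing groups.

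**2. Possible comparison families (an assumption, because the protocol names none).**
- All pairs of 36 groups: 36 × 35/2 = 630.
- Pairs differing in one factor only: 18 gender pairs + 12 × 3 = 36 race pairs + 6 × 15 = 90 age pairs = 144.
- Race pairs within age and gender: 36.
- Gender pairs within age and race: 18.
- White v African-American within age and gender: 6 × 2 = 12.

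**3. Power at 80 v 80.** Two-sided level 0.05/m (Bonferroni), noncentral t with 158 df, noncentrality d × √(80/2), which is 3.162 for d = 0.5. The differences 0.5 and 0.3 SD are assumed, and the Z-scores are taken to come from a common reference.

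| Comparisons m | Critical t | Power, 0.5 SD | Power, 0.3 SD |
|---|---|---|---|
| 630 | 4.05 | 19% | 2% |
| 144 | 3.66 | 32% | 4% |
| 36 | 3.26 | 47% | 9% |
| 18 | 3.04 | 55% | 13% |
| 12 | 2.91 | 60% | 16% |
| 1 (unadjusted) | 1.98 | 88% | 47% |

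The Tukey method for all 36 groups gives 25% at 0.5 SD. With 630 pairs, 80% power needs a difference of (3.946 + 0.842) × √(2/80) = 0.76 SD.

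**4. Contrasts pooled over the other factors.**
- Gender: 18 × 80 = 1440 v 1440, 95% half-width 1.96 × √(2/1440) = 0.073 SD.
- White v African-American: 12 × 80 = 960 v 960, half-width 1.96 × √(2/960) = 0.089 SD; 80% power at (1.96 + 0.842) × √(2/960) = 0.128 SD.
- Power for 0.5 SD is near 100% in both, even at level 0.05/630.

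**5. Effect of merging two equal-sized normal groups.**
- *Means 0.5 SD apart, equal SDs.* Merged SD = √(1 + 0.5²/4) = 1.031, so Z = +2 lies 2.062 above the midpoint. Higher group: P(N > 2.062 − 0.25 = 1.812) = 3.5%. Lower group: P(N > 2.312) = 1.0%. Nominal: 2.3%.
- *Equal means, SD ratio 1.3 (assumed).* Merged SD = √((1 + 1.69)/2) = 1.160, so the limits are ±2.319. Narrower group: 2 × P(N > 2.319) = 2.0% outside. Wider group: 2 × P(N > 2.319/1.3 = 1.784) = 7.4% outside. Nominal: 4.6%. With equal means the t-test rejects only at about its own level, so it gives no protection here.

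**The case against.** Several stronger readings are tempting, and the documents do not support them.

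- *Groups are merged whenever the test is not significant.* The text says they may be combined. This is permission, not an automatic rule. What stands is that no other criterion guides its use.
- *Real differences of half an SD are usually merged away.* That needs a family of about 36 comparisons or more. With 18 or 12, power is 55% or 60%, so most such differences would be found. The male/female example can also be read as a contrast pooled over age and race, where power is near 100%.
- *Section 10 contradicts the test.* It says "The study will have enough power to determine" White v African-American differences. That is a statement about the study, not about each age-by-gender cell, and the pooled contrast reaches 80% power at about 0.13 SD. A calculation is absent, but the sentence is not shown to be wrong.

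It is also fair that the family, the adjustment method and any margin may be set in a statistical analysis plan that is not at hand, that Section 6.1.1 derives all 36 means and SDs before any merging, and that Section 6.5 gives a route for revision. These points lower the severity. They do not remove the defect, because the protocol itself fixes the test, the direction of error control and the non-significance criterion.

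**Conclusion.** The point holds and should be fixed before analysis. Under every reading of the comparison family, non-significance licenses merging, a stricter adjustment makes it easier, and group SDs go uncompared.

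The size of the risk is open: the chance of missing a true 0.5 SD difference runs from 81% (630 pairs) to 40% (12 pairs) at 80 v 80, and is close to nil for pooled contrasts. If such groups are merged, upper-tail rates become 3.5% and 1.0% instead of 2.3%. An SD ratio of 1.3 gives 7.4% and 2.0% outside ±2 instead of 4.6%.

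This rests on 80 evaluable children per group, two-sided 0.05 with Bonferroni, normality, equal group sizes, and the assumed differences of 0.5 SD and 1.3. It also assumes Z-scores from a common reference. If each child's Z used its own group's mean and SD from Section 6.1.1, every group would have mean 0 and SD 1 by construction, and the t-test could find nothing.

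**What to change.** In Sections 6.1.2 and 6.3, replace the non-significance rule as follows.

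- Fit one pooled model per measurement on Z-scores from a common reference, with age, gender and race terms for both mean and SD and the interactions with age.
- Collapse a factor only if the confidence interval for its mean difference and that for its SD ratio lie inside margins preset by the sponsor, and the age interactions show no relevant difference in any age band.
- Drop the multiplicity adjustment for merging.

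The age interactions are needed. Take an illustrative margin of ±0.25 SD and a true gender difference of 0.5 SD confined to two of the six age bands. The average is 0.5 × 2/6 = 0.167, and 0.167 + 0.073 = 0.240 lies inside the margin, so a main-effects rule could merge it.

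The margins must suit the sample. Single groups at 80 v 80 have a half-width of 1.96 × √(2/80) = 0.31 SD and could never meet ±0.25. Within one age band the half-width is 1.96 × √(2/240) = 0.18 SD for gender and 1.96 × √(2/160) = 0.22 SD for White v African-American.

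Optionally, Section 10 can state that its power refers to the pooled race contrast (960 v 960, 80% power at about 0.13 SD).

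The cost is wording and some modelling work, with no extra patients. The downside is that more groups may stay separate, giving more reference equations.
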